This protocol template is intended for use in clinical studies which **are not** Clinical Trials of Investigational Medicinal Products (CTIMPs) that are Sponsored or Co-Sponsored by the University of Dundee and/or NHS Tayside.

All sections may be adapted to suit a particular trial/study.

Some sections may be added as required by the specific trial/study.

All blue/red instruction text is for guidance only and must be removed.

Trial/Study Protocol

Full study title: "Studying Pregnancy's VAscular and Retinal Changes" SPARC

Short Title /Study Acronym	"Studying Pregnancy's VAscular and Retinal Changes" SPARC
Sponsor	University of Dundee
Sponsor ID	2-021-25
Funder	University of Dundee
Chief Investigator	CI: [name]
Principal Investigator	PI: [name] (PhD student)
	2 nd Academic supervisor: [name]
	3d Academic supervisor: [name]
IRAS Number	347685
Version Number and Date	1.0
	13/3/2025

PROTOCOL APPROVAL

Insert trial/study title: "Studying Pregnancy's VAscular and Retinal Changes" SPARC

Signatures

The undersigned confirm that the following protocol has been agreed and approved by the Sponsor and that the Chief Investigator agrees to conduct the trial/study/study in compliance with this approved protocol and will adhere to the principles of GCP, the Sponsor SOPs, and any other applicable regulatory requirements as may be amended from time to time.

[name]	[name]	01/02/2025
Chief Investigator	Signature	Date
[name]	[name]	01/02/2025
Individual Responsible for Statistical Review	Signature	Date

LIST OF ABBREVIATIONS

AE	Adverse Event	
CI		
	Chief Investigator	
CNORIS	Clinical Negligence and Other Risks Indemnity Scheme	
CRF	Case Report Form	
DMC	Data Monitoring Committee	
GCP	Good Clinical Practice	
ICF	Informed Consent Form	
IF	Incidental Findings	
ISF	Investigator Site File	
PI	Principal Investigator	
REC	Research Ethics Committee	
SAE	Serious Adverse Event	
SOP	Standard Operating Procedures	
S/TMF/SMF	Trial Master File/Study Master File	
T/SMG	Trial Management Group	
TSC	Trial Steering Committee	

SUMMARY/SYNOPSIS

Trial/Study Title (including acronym)	Studying Pregnancy's VAscular and Retinal Changes (SPARC)	
Trial/Study Design	Prospective imaging study	
Trial/Study Population	Pregnant women	
Sample Size	P. 44	
Planned Trial/study Period	24 months	
Clinical phase duration	During Pregnancy	
Follow up phase duration or specify none	n/a	
Primary	Objectives To investigate the potential of retinal imaging technology to assess endothelial function in women during pregnancy, in order to evaluate the effect of GH on maternal CV function.	Outcome Measures Primary Outcome Measures: 1. Retinal Vascular System 2. Endothelial Function 3. Cardiovascular Function biomarkers Secondary Outcome Measures: 1. Pregnancy-Related Health Outcomes 2. Maternal Health
Secondary	Objectives Study – Aim: Investigate whether retinal imaging is able to capture endothelial dysfunction in women who have complicated pregnancy. Endothelial function measured using retinal imaging and ultrasound pulse-wave Doppler and measured in correlation with serum biomarkers.	Outcome Measures 1. Primary Outcome Measures - Retinal Vascular Health measurements - Ultrasound Pulse-Wave Doppler Findings - Blood Biomarkers 2. Secondary Outcome Measures - Long-term Cardiovascular Risk Indicators
Optional Inclusion Criteria	Prospective imaging study 1- Women aged 18 or above 2- Women who are pregnant after 8 weeks 3- Women must be able to give written informed consent (ICF) Note: Women that are diagnosed with gestational hypertension (after 12 weeks) will be included. Includes the following hospital: NINEWELLS HOSPITAL	
Optional Exclusion Criteria	1- Maternal age less than 18 years 2- Women who are not capable of giving informed consent (ICF).	

Studying Pregnancy's VAscular and Retinal Changes (SPARC), Non CTIMP Protocol (SPARC) During Preg <v1.0 13/3/2025>; IRAS: 347685

5.Known retinal or eye disorders	 3- Pre-existing chronic hypertension or cardiovascular diseases diagnosed prior to the index pregnancy. 4. Women that have chronic hypertension at their booking visit (before 12 weeks)
hypertensive therapy, anticoagulants).	5.Known retinal or eye disorders6. Use of medications affecting endothelial function (e.g., ongoing anti-

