2 STUDY OBJECTIVES & OUTCOMES

To establish vascular changes in retinal and ophthalmic Doppler in normal and pregnancies associated with gestational hypertension. We hypothesise that women with GH or foetal growth restriction will have increased endothelial dysfunction, as shown by retinal and ultrasound imaging.

Table 1: Primary Objectives and Outcome Measures

Primary Objective:	Outcome Measure:	Timepoint of outcome measured
Objective: To investigate the potential of retinal imaging technology to assess endothelial function in women during pregnancy, in order to evaluate the effect of GH on maternal CV function.	 Retinal imaging Biomarkers of Endothelial Function Ultrasound Pulse- Wave Doppler 	mild-late pregnancy for women with GH and normal pregnancies.

Table 2: Secondary Objectives and Outcome Measures

Secondary Objective:	Outcome Measure:	Timepoint of outcome measured
Study - Aim: A prospective study to image the retina in early and mid-stages of gestation and track pregnancy outcome in correlation with serum biomarkers and standard diagnostic measurement (ultrasound pulse-wave doppler) imaging.	 Retinal imaging Biomarkers of Endothelial Function Ultrasound Pulse- Wave Doppler 	mild-late pregnancy for women with GH and normal pregnancies.

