6 STATISTICS AND DATA ANALYSIS

Descriptive statistics will be used in this study. To compare between groups, we will use a t-test and binary logistic regression, depending on the situation. Logistic regression analysis will be conducted to evaluate and account for any confounding factors. In order to validate the non-invasive techniques, a Bland-Altman analysis will be conducted to evaluate the comparability of the methods. Regression analysis to identify predictors of pregnancy outcomes. The Statistical analysis will be performed in SPSS (SPSS Statistics. 2022. Version 29.0.0.0. International Business Machines Corporation, New York, United States).

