6.1 SAMPLE SIZE CALCULATION

Comparison of CV function in women at high and low risk of PE

Ninewells has approximately 4500 births per year with approximately 450 cases of gestational hypertension. Our goal here is to describe the evolution of maternal microvascular function in women that develop gestational hypertension comparing to those that do not develop gestational hypertension.

Our previously published studies (Khan et al 2005 Hypertension, https://doi.org/10.1161/01.HYP.0000186328.90667.95; Changes in Endothelial function preceded the clinical disease in women in whom PE develops) demonstrated changes in microvasculature at 26 weeks in n=15 women with PE compared to normotensive (n=54). Using this previous data, a Power Analysis (G*power)) -A Piori carried out to compute the required sample size for the Wilcoxon-Mann Whitney test (2 groups). With

αα

= 0.05 and power of 95% to detect an effect size of 25%, each group requires a n=11.

As this is a prospective study to obtain measurements at the onset of gestational hypertension, we predict we need to recruit 110 women to obtain the 10% of women that develop gestational hypertension. Women who are high-risk or that have been newly diagnosed, i.e. attending hypertensive clinics, will be recruited

Further details:

 During-Pregnancy: Recruit 110 women to account for the 10% who will develop gestational hypertension.

Sample size required for each group (high vs. low risk):11 women per group

• Total Participants:

-During-Pregnancy: 110 women (recruitment to achieve the final sample of 22 women)

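### No single primary variable, visit or decision rule is fixed, so the alpha of 0.05 and the 95% power in section 6.1 cannot be attributed to the primary objective

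*Protocol*

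**What the plan says.** The primary row of the protocol synopsis lists "1. Retinal Vascular System 2. Endothelial Function 3. Cardiovascular Function biomarkers". In section 2, the table headed "Table 1: Primary Objectives and Outcome Measures" gives a list that only partly agrees: "Retinal imaging Biomarkers of Endothelial Function Ultrasound Pulse- Wave Doppler". Table 2 gives the same three entries for the secondary objective. The synopsis row for secondary objectives also has its own sub-list labelled as primary outcomes (retinal, Doppler, blood biomarkers).

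The hypothesis in section 2 is that affected women "will have increased endothelial dysfunction, as shown by retinal and ultrasound imaging".

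Section 6 says: "To compare between groups, we will use a t-test and binary logistic regression, depending on the situation". It names no outcome for these comparisons.

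Section 6.1 used a power program to "compute the required sample size for the Wilcoxon-Mann Whitney test (2 groups"), with alpha 0.05 and "power of 95% to detect an effect size of 25%, each group requires a n=11". The only outcome mentioned there is microvascular change in an earlier study by the same group, of 15 women with pre-eclampsia and 54 normotensive women. No variable, mean or SD is given.

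**The concern.** An alpha and a power belong to a defined test of a defined variable. Here the test is defined by its size only. The listed primary outcomes are families, and sections 3 and 3.1 show what they hold: a retinal measure, sFlt-1, PlGF, endothelin-1, carotid ultrasound and ophthalmic artery Doppler. That is at least six quantities before counting two eyes, vessel elasticity or the two possible visits (weeks 10 and 20 in section 3.5).

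With 22 women analysed and the list left open, whichever measure reached significance could be presented as the primary result, with 0.05 and 95% quoted beside it. An SAP may settle multiplicity adjustment. The choice of primary variable and its match to the sample size belong in the protocol, and an SAP cannot remove the disagreement between the protocol's own lists.

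**Working it through.** **1. The lists side by side**

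| Place | Retinal | Endothelial function / blood markers | Third entry |
|---|---|---|---|
| Synopsis, primary row | yes | endothelial function | cardiovascular function biomarkers |
| Table 1 (primary) | yes | biomarkers of endothelial function | pulse-wave Doppler |
| Table 2 (secondary) | yes | biomarkers of endothelial function | pulse-wave Doppler |

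The first two columns broadly agree and the third does not. Tables 1 and 2 are identical, so every Table 1 outcome is both primary and secondary. No row names one variable or one visit.

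**2. The plan's own figure**

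Inputs from section 6.1: alpha 0.05, power 95%, effect size 25%, 11 per group, one Wilcoxon-Mann-Whitney test. Sidedness is not stated.

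- Reading 25% as a standardised difference of 0.25, two-sided: n = 2(1.960 + 1.645)² / 0.25² = 2 × 12.996 / 0.0625 ≈ 416 per group. With the rank-test efficiency of 3/π and the noncentral t it is 437. One-sided, the normal approximation gives 347. The stated 11 is not reproduced.
- Working backwards, 11 per group with 95% power needs a standardised difference of about 1.66 (Wilcoxon, normal data, two-sided), or 1.17 to 1.76 across one- and two-sided tests and several distributions.
- Reading 25% as a relative difference, 1.66 implies an SD of 25/1.66 ≈ 15% of the mean (14 to 21% across the same variants). The protocol gives no SD, so this cannot be checked.

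This matters here only because it shows that section 6.1 has no input belonging to a listed outcome.

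**3. What each decision rule would do**

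Assumptions: m outcomes each compared between groups at 0.05 with 11 per group; a common correlation of 0, 0.5 or 0.8 (not in the protocol); for power, every outcome has exactly 95% power alone. Values at correlation 0 are exact and the others are simulated t-tests.

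*Any one significant result counts.* False-positive risk = 1 − 0.95^m.

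| m | correlation 0 | 0.5 | 0.8 |
|---|---|---|---|
| 3 | 1 − 0.857 = 14.3% | 12 to 13% | 10% |
| 6 | 1 − 0.735 = 26.5% | 21% | 14% |

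The chance of at least one success is 1 − 0.05³ = 99.99% for three independent tests and about 98% at correlation 0.8. Alpha is lost; power is not.

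*All must be significant.* The type I error stays at or below 0.05. Joint power = 0.95^m: 85.7% for three and 73.5% for six if independent, about 91% and 87% at correlation 0.8.

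*Alpha is split.* At 0.05/3 = 0.0167, power per outcome is about 87%; at 0.05/6 = 0.0083, about 79%. Both use the back-solved difference of 1.66, which is not in the protocol, so they are illustrations. The chance that at least one of three succeeds would remain about 95% or higher.

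*Ordered testing.* Both stated figures hold for the first outcome in the order only, and no order is given.

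**The case against.** The strongest reply is that this is an exploratory study. The objective is to investigate the potential of a technique, section 6 opens with descriptive statistics, section 6.2 plans correlations and regressions, and section 3.5 says the data will inform a future power analysis. On that view multiplicity is not a protocol matter. This weakens any claim of error inflation, but it does not cancel the formal 0.05 and 95% statement in section 6.1, which still needs an outcome.

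A reader might infer that each family is separately tested and that both alpha and power fail. The documents do not support that. Section 6 does not say which outcomes are compared, so separate testing is an inference. Alpha inflation and power loss also come from different rules: under any-of-several alpha rises but the chance of success does not fall, and under all-of-several or a split alpha is kept. Nor is a chance finding likely in the ordinary sense: at most about 26% for six independent tests, and less if the outcomes correlate, as section 6.2 expects.

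It is also fair that section 2 gives ophthalmic Doppler equal weight with retinal imaging, so choosing a retinal variable is partly a judgement. The objective in both the synopsis and Table 1 speaks of retinal imaging, which is why that choice fits best.

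**Conclusion.** The point holds in a limited form. The protocol fixes no primary variable, no visit and no rule for combining its primary families. Its lists do not fully agree, and Table 1 and Table 2 give the same measures both ranks. The alpha of 0.05 and the 95% power are therefore attached to no listed outcome.

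The size depends on a rule the protocol does not give. It is a false-positive risk of about 10 to 14% for three tests or 14 to 26% for six if any success counts. If all must succeed, joint power is about 86 to 91% for three outcomes, with alpha kept. The first range rests on assumed correlations from 0.8 to 0. The second also assumes 95% power for each outcome alone, which section 6.1 does not establish.

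**What to change.** - In the synopsis and Table 1, name one retinal variable at one visit as the sole primary outcome for gestational hypertension versus none.
- List the Doppler and serum measures as secondary, reported with confidence intervals. Make the synopsis, Table 1 and Table 2 agree.
- In section 6.1, apply alpha 0.05 to the primary variable only. State 95% power only if the assumed difference and SD for that variable are given and support 11 per group; otherwise restate the power. The existing figure should not simply be relabelled, because the protocol gives no retinal mean or SD.

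The first two changes are wording and need no extra data. The third needs a sourced difference and SD, and may show lower power than is now claimed. The downside is small: claims on Doppler and biomarkers become secondary.

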3.2 STUDY RECRUITMENT

Women will be recruited who are pregnant for assessment in mid and/or late term. The outcome of the pregnancy will be tracked.

Women will be invited to join the study by the care teams in clinics at Ninewells and the Tayside area

- Obstetric Antenatal Clinics (Recruitment will be overseen [name] [name] (UoD/NHS) and [name] (NHS))
- Assisted conception clinic (Recruitment will be overseen [name] [name] (UoD/NHS))
- Hypertension Clinic (Recruitment will be overseen by [name](UoD/NHS))

This is a prospective study. Control groups will be made up of women that do not get gestational hypertension. Pregnant women that attend the Hypertension clinic may be recruited due to their gestational hypertension. Women attending the Obstetric Antenatal Clinics and Assisted conception clinics will be identified with clinical collaborators including [name] [name], [name] and [name]. To be able to identify potential participants from their medical records Caldicott Approval will be sought. Only with Caldicott approval will the medical records be searched.

The care team will approach or invite participation in the study in clinic. Any invitation will introduce the potential patient to the study team and will include a PIS. The care team will not follow up with patients to determine their interest in the study.

The study team will include Clinical Research Centre nurses that will assist with recruitment. The study team will confirm recruitment via a short telephone conversation prior to them attending Ninewells for the study visit.

Advertisement of the study and identification of potential participants will be identified from the NHS Tayside clinics at Ninewells Hospital including maternity clinics, ultrasound department, antenatal clinics, day assessment unit, Assisted Conception Unit, https://www.acudundee.org/ hypertension and diabetics clinics among others. Caldicott approval will be gained to allow identification of potential participants from medical records and clinical lists by the care team. Letters with PIS may be sent to the potential participants from the clinical team. We chose the following sites, since this is where pregnant women obtain their routine care.

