3.14 INCLUSION CRITERIA

Case group:

Women who

- Are Aged 18 or above
- Are Able to give written informed consent (ICF)
- Are in mid-to-late gestation.
- Were diagnosed with Gestational hypertension (systolic BP ≥ 140 mmHg or diastolic BP ≥ 90 mmHg) in their pregnancy.
- Do not have cardiac or ophthalmic disorders

Control group:

Pregnant women that are

- Aged 18 or above
- Able to give written informed consent (ICF)
- Have no gestational hypertension (normal pregnancy/ nonhypertension)
- Do not have cardiac or ophthalmic disorders

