4 PARTICIPANT SELECTION AND ENROLMENT

For the following reasons, there is very little chance of researcher bias: 1. Objective examinations are used to measure the vascular function in pregnancy non-invasively; the majority of these tests are automated. 2. The woman's own attending clinicians will diagnose pregnancy problems, like PE, gestation hypertension and gestation diabetic mellitus based on the hospital's established criteria.

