9 ADVERSE EVENTS

Serious Adverse A serious adverse event is any untoward medic occurrence that:	Adverse Event (AE)	Any untoward medical occurrence in a clinical research participant which does not necessarily have a causal relationship with study participation
existing hospitalisation		 results in death is life threatening requires hospitalisation or prolongation of existing hospitalisation results in persistent or significant disability or incapacity

9.1 **DEFINITIONS**

The following definitions will be used in this study, based on the American College of Obstetrics and Gynaecology (ACOG, 2002).

- 1- Chronic hypertension: BP ≥140/±90 mm Hg before pregnancy or before the 20th week of gestation
- 2- Preeclampsia-eclampsia: A pregnancy-specific disorder that is a multisystem disease characterized by hypertension ≥140/±90 mm Hg on ≥2 occasions at least 6 hours apart, and proteinuria ≥300 mg in a

24-hour urine collection, after 20 weeks' gestation. The convulsive form of PE is eclampsia and affects 0.1% of all pregnancies.

- 3- Preeclampsia superimposed on chronic hypertension: Up to 30% of women with chronic hypertension develop PE, as heralded by the occurrence of de novo proteinuria in the third trimester. In women with chronic hypertension and preexisting proteinuria (ie, before 20 weeks of gestation), the diagnosis of superimposed PE is likely with any of the following findings: sudden increase in proteinuria, sudden worsening of previously well-controlled BP, new-onset thrombocytopenia, or elevated liver function tests.
- 4- Gestational hypertension: New onset of hypertension ≥140/±90 mm Hg on ≥2 occasions at least 6 hours apart, after 20 weeks' gestation, in the absence of proteinuria, <300 mg in a 24-hour urine collection. If BP returns to normal by 12 weeks postpartum, the diagnosis of transient hypertension of pregnancy can be assigned. If elevated BP persists, the diagnosis of chronic hypertension is made.

Other conditions:

Pre-gestational diabetes

- Type I insulin-requiring diabetes
 - Participant taking (or prescribed) insulin prior to pregnancy
- Type II non-insulin requiring diabetes
 - Participant taking (or prescribed) oral diabetic agents prior to pregnancy

Gestational diabetes

- Prior pregnancy affected by gestational diabetes
 - No interval diagnosis of diabetes
- Current pregnancy affected by gestational diabetes

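### The protocol classifies the same woman differently in different sections, so pre-eclampsia has no consistent group and normotensive growth restriction defaults to control

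*Protocol*

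**What the plan says.** **Gestational age.** The synopsis says "Women that are diagnosed with gestational hypertension (after 12 weeks) will be included", and its exclusions name "Women that have chronic hypertension at their booking visit (before 12 weeks". Section 9.1, which presents its definitions as those used in this study, defines chronic hypertension as present "before pregnancy or before the 20th week of gestation" and gestational hypertension (GH) as new onset after 20 weeks.

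**Blood pressure and proteinuria.** Section 3.14 admits to the case group women who "Were diagnosed with Gestational hypertension (systolic BP ≥ 140 mmHg or diastolic BP ≥ 90 mmHg) in their pregnancy". Section 9.1 requires raised pressure on at least two occasions 6 or more hours apart, and "in the absence of proteinuria, <300 mg in a 24-hour urine collection". It lists pre-eclampsia (PE) as a separate entity.

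**Who diagnoses.** Section 4 leaves diagnosis to the attending clinicians, "based on the hospital's established criteria".

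**Grouping.** Section 3.12 assigns women to one of two groups once the outcome is known. Section 3.2 says "Control groups will be made up of women that do not get gestational hypertension". Section 3.14 adds that controls are non-hypertensive and have a normal pregnancy, and the control exclusions in 3.15 carry the 140/90 threshold.

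**Hypothesis.** Section 2 expects that "women with GH or foetal growth restriction will have increased endothelial dysfunction".

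**Case exclusion.** Section 3.15 lists hypertension during pregnancy among the reasons to exclude a woman from the case group.

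**The concern.** Group membership defines the case-control comparison, and it is assigned after the outcome is known. If the text supports more than one assignment for the same woman, whoever classifies must choose between rules when the imaging data may already exist. Two kinds of pregnancy matter most. PE is the condition on which the sample size reasoning in Section 6.1 rests (PE against normotensive women), yet the two-group scheme gives it no settled place. Normotensive growth restriction is named in the hypothesis as affected, yet the control rule takes it into the reference group. Affected women among the controls would shrink the difference the study is looking for.

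**Working it through.** No figure in the plan is in dispute, so the check is to run five kinds of pregnancy through the rules as written.

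| Pregnancy | Case rule, 3.14 | Control rule in 3.2, read with 9.1 | 9.1 read with control criteria in 3.14 and 3.15 |
|---|---|---|---|
| First hypertensive at 12-20 weeks | Case by threshold (also a case in the synopsis) | Control (chronic by 9.1, so not GH) | Neither |
| One raised reading after 20 weeks, not repeated | Meets the bracketed threshold | Control | Neither (140/90 bars her from controls) |
| PE | Case by threshold | Control | Neither |
| Normotensive growth restriction | Not a case | Control | Control, unless the undefined phrase about normal pregnancy excludes her |
| GH exactly as in 9.1 | Case | Not a control | Case, but removed by the 3.15 case exclusion read literally |

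The first three rows each give three different answers. In the fourth, the only text against control status is an undefined phrase.

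The 12-20 week interval overlaps both visit windows in Section 3.5: week 10 ± 3 is weeks 7 to 13, and week 20 ± 3 is weeks 17 to 23.

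**Numbers from Section 6.1.** 450 / 4500 = 10%; 110 × 10% = 11 expected cases; 110 − 11 = 99 expected non-cases. The 10% applies to whichever definition of GH produced the 450. Recruiting from hypertension clinics, as the section also plans, could raise the share of cases.

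**Direction of bias.** Let Δ be the true case-control difference and c the fraction of controls who carry the full case shift (an assumption). The expected observed difference is (1 − c) × Δ. For one such woman:
- among 11 controls (Section 3.13): c = 1/11 = 9.1%, leaving 90.9% of Δ;
- among 99 non-cases, if all are analysed: c = 1/99 = 1.0%, leaving 99.0% of Δ.

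This gives direction and scale per woman only. Converting it to power needs the rates of PE and growth restriction and an SD. The protocol gives none of these: Section 6.1 states an effect size of 25% without an SD.

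**The case against.** A reader might infer that the plan puts PE into the control group. The documents do not support that as a general statement. It follows only from the one-line rule in 3.2 combined with the definitions in 9.1. The control criteria in 3.14, the 140/90 control exclusion in 3.15 and the reference in Section 3 to normotensive comparators all keep hypertensive women out. What stands is narrower: PE has no consistent group.

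Section 3.14 can also be read as shorthand. It requires a diagnosis and gives the threshold only in brackets, so two readings and absence of proteinuria could be the fuller form of the same rule. That reading is fair, but 3.14 does not refer to 9.1, and Section 4 points to hospital criteria whose content is not shown. The 12 against 20 week conflict cannot be resolved in this way.

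On growth restriction, 3.14 and Section 2 do speak of normal pregnancies. If that phrase were defined to exclude growth restriction, the problem would disappear. It is not defined.

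Finally, not every analysis depends on the groups: the aim in Section 6.2 is correlation among retinal, ultrasound and blood measures. The point is confined to the case-control comparison and to models with GH as outcome.

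**Conclusion.** The concern holds in this form. The 12 against 20 week boundary is a direct contradiction. The rules on repeat readings and proteinuria differ between 3.14 and 9.1 and are not linked. PE can be case, control or neither. Normotensive growth restriction defaults to control against the study's own hypothesis, which would bias the group difference toward zero if the hypothesis is true. The 3.15 case exclusion, taken literally, empties the case group.

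The size cannot be fixed from the protocol. Per affected woman, attenuation lies between about 1% (99 controls) and 9% (11 controls), assuming she carries the full case shift. A stated loss of power would need a contamination rate and an effect in SD units that the document does not contain, so none is claimed.

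**What to change.** Amend the synopsis and Sections 3.2, 3.14, 3.15, 4 and 9.1 so that one research classification governs group assignment everywhere. Section 9.1 already claims that role, so it is the natural place to hold it. Which gestational boundary and diagnostic criteria it should contain is for the sponsor to settle; this review does not choose between them. Within that amendment:

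- State one explicit allocation for PE that keeps it out of the control group. Pooling it with GH would change the question from GH to hypertensive disorders more broadly, so the choice should be deliberate.
- Define controls as pregnancies that remain normotensive to delivery and are without growth restriction, and report growth restriction separately.
- Reconcile the 3.15 case exclusion on hypertension during pregnancy with the 3.14 case inclusion.

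The cost is wording and the approvals that Section 11.1 requires for any amendment. A few women would leave a control pool of about 99 expected non-cases, of whom Section 3.13 needs 11.
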